5.2 EXCLUSION CRITERIA

Participants are excluded from the study if any of the following criteria apply:

Medical Conditions

1. Participants with a history or clinical evidence of central nervous system (CNS) primary tumors or metastases including leptomeningeal metastases unless they have been previously treated, are asymptomatic, and have had no requirement for steroids or enzyme-inducing anticonvulsants in the last 14 days before screening.
2. Participants with non-irradiated lesions > 2 cm at critical sites (e.g., paraspinal, paratracheal) where tumor swelling induced by RO7172508 is expected to lead to significant complications.
3. Participants with another invasive malignancy in the last 2 years (with the exception of basal cell carcinoma and tumors deemed by the Investigator to be of low likelihood for recurrence).
4. Evidence of significant, uncontrolled concomitant diseases that could affect compliance with the protocol or interpretation of results or contraindicate the use of an investigational drug, including diabetes mellitus and history of relevant pulmonary disorders.

Diagnostic Assessments

5. Uncontrolled hypertension (systolic blood pressure [SBP] > 150 mmHg and/or diastolic BP [DBP] > 100 mmHg), unstable angina, congestive heart failure (New York Heart Association (NYHA) > 1, serious cardiac arrhythmia that requires treatment with the exceptions of atrial fibrillation and paroxysmal supraventricular tachycardia, and history of myocardial infarction within 6 months of enrollment.
6. Active or uncontrolled infections.
7. Known hepatitis B or C (active replicating).
8. Major surgery or significant traumatic injury < 28 days prior to the first RO7172508 administration (excluding biopsies) or anticipation of the need for major surgery during study treatment.
9. Dementia or altered mental status that would prohibit informed consent.
10. Baseline corrected QT interval of > 470 ms. Participants with baseline resting bradycardia < 45 beats per minute (bpm) or baseline resting tachycardia > 100 bpm.
11. Radiotherapy within the last 28 days prior to the first RO7172508 administration with the exception of limited-field palliative radiotherapy.
12. Presence of bilateral lung lesions with either > 3 lesions per lung or ≥ 1 lesion per lung with a diameter > 3 cm (*only unequivocal lesions of > 1cm are to be counted for this criterion, unless there is miliary metastatic-type diffuse disease, then these participants are ineligible*).

Prior/Concomitant Therapy

13. Concurrent therapy with any other investigational drug (defined as treatment for which there is currently no regulatory authority-approved indication) < 28 days prior to the first RO7172508 administration.
14. Last dose with an immunostimulating or immunosuppressive therapy (e.g., IFN- α , IFN- β , IL-2, etanercept, infliximab, tacrolimus, cyclosporine, or mycophenolic acid) < 28 days prior to the first RO7172508 administration.
15. Last dose of anti-CTLA4, anti-PD-L1, or anti-PD1 < 180 days prior to the first RO7172508 administration.
16. Expected need for regular immunosuppressive therapy (i.e., for organ transplantation, chronic rheumatologic disease) within 28 days prior to the first RO7172508 administration.
17. Regular dose of corticosteroids within 28 days prior to Day 1 of this study or anticipated need for corticosteroids that exceeds prednisone 10 mg/day or equivalent within 28 days prior to the first RO7172508 administration. Inhaled and topical steroids are permitted.
18. Prior treatment with a bispecific T-cell engaging drug targeting CD3e and/or CEA.

Other Exclusions

19. Known hypersensitivity to any of the components of RO7172508.

Specific Exclusion Criteria if Pre-treatment with Obinutuzumab is Implemented

20. *Known HIV (HIV testing will be performed at screening if required by local regulations)*
21. *Positive test results for chronic HBV infection (defined as positive HBsAg serology), HBcAb indicating an active viral infection and positive test results for HCV (HCV antibody serology testing).*
22. *Participants positive for HCV antibody are eligible only if polymerase chain reaction (PCR) is negative for HCV ribonucleic acid (RNA).*
23. *History of progressive multifocal leukoencephalopathy.*
24. *Active TB requiring treatment within 3 years prior to baseline.*
25. *Latent TB diagnosed during Screening.*
26. *Positive test results for human T-lymphotropic virus 1 (HTLV 1)*
27. *HTLV testing is required in participants from endemic countries (Japan, countries in the Caribbean basin, South America, Central America, sub-Saharan Africa, and Melanesia)*
28. *Known hypersensitivity to any of the components of obinutuzumab.*

5.3 LIFESTYLE CONSIDERATIONS

There are no study-specific restrictions to meals and dietary requirements.

5.4 SCREEN FAILURES

Screen failures are defined as participants who consent to participate in the clinical study but are not subsequently entered in the study.

The Investigator will maintain a screening log to record details of all participants screened and to confirm eligibility or record reasons for screening failure.

Individuals who do not meet the criteria for participation in this study (screen failure) may be re-screened once providing they have not received the study drug and after discussion and agreement with the Sponsor. Re-screened participants should be assigned the same participant number as for the initial screening. Some essential procedures, such as biopsies, may be used from the initial screening period in agreement with the Sponsor. In the event that a fresh biopsy is taken during the screening period and the participant is not enrolled into the study, the formaldehyde-fixed paraffin-embedded (FFPE) biopsy block can be returned to the site upon site request.

5.5 RECRUITMENT PROCEDURES

Participants will be identified for potential recruitment by the Investigator and referring physicians using pre-screening enrollment logs, clinical databases and Institutional Review Board (IRB)/Independent Ethics Committee (IEC) approved newspaper/radio/social-media advertisements prior to consenting to take place on this study.

6. TREATMENTS

Study treatment is defined as any investigational treatment(s), marketed product(s), placebo, or medical device(s) intended to be administered to a study participant according to the study protocol.

The investigational medicinal products (IMP) required for completion of this study (RO7172508, *obinutuzumab* and tocilizumab) will be provided by the Sponsor. Administration of study treatment will be at the study centers under supervision of qualified site staff.

6.1 TREATMENTS ADMINISTERED

Table 11 summarizes the treatments administered.

Table 11 RO7172508 Summary of Treatments Administered

Study Treatment Name:	Part I RO7172508	Part II RO7172508
Dosage Formulation:	Solution for infusion and injection	Solution for infusion and injection
Unit Dose Strength(s)/Dosage Level(s):	20 mg/mL	20 mg/mL
Dose:	65 µg up to a maximum of 1.6 mg	1.6 mg up to a maximum of 400 mg IV 2 mg up to a maximum of 160 mg SC
Route of Administration:	IV	IV and SC
Dosing Instructions:	see Pharmacy Manual	see Pharmacy Manual
Packaging and Labeling:	Study treatment will be provided in a carton box (one labeled vial per box). Each carton box will be labeled as required per country requirement.	Study treatment will be provided in a carton box (one labeled vial per box). Each carton box will be labeled as required per country requirement.

Guidelines for dosage modification and treatment interruption or discontinuation are provided in Section 6.6 or Section 7, respectively.

Please see the [RO7172508 Investigator's Brochure](#) and Pharmacy Manual for more details.

Administration of Obinutuzumab

The obinutuzumab Drug Product will be supplied by the Sponsor as a 50 mL single dose glass vial containing 1000-mg liquid concentrate in 40 mL (25 mg/mL) for infusion. In addition to the drug substance, the liquid is also composed of histidine/histidine-HCl, trehalose and poloxamer 188 (see Table 12).

Obinutuzumab will be administered either as a single dose of 2000 mg 7 days (D-7) before the first dose of RO7172508 (C1D1) or two doses of 1000 mg over days 6 and 7 days (D-6 and D-7) before the first dose of RO7172508 (C1D1).

For information on the formulation and handling of obinutuzumab, refer to the pharmacy manual and Obinutuzumab [Investigator’s Brochure](#).

Table 12 Obinutuzumab Summary of Treatment Administered

Study Treatment Name	Obinutuzumab
Dosage Formulation	Concentrate for solution for IV infusion
Unit Dose Strength(s)/Dosage Level(s)	25 mg/mL
Dose	2000 mg or split doses of 2x 1000 mg
Route of Administration	IV
Dosing Instructions	see Pharmacy Manual
Packaging and Labeling	Study treatment will be provided in a carton (one labeled vial per box). Each carton will be labeled as required per country requirement.

Administration of Tocilizumab

Administration of tocilizumab is based on clinical presentation of CRS and should follow the guidelines stated in Section [8.3.8.1](#).

Please see the [tocilizumab Investigator’s Brochure](#) and Pharmacy Manual for more details.

Table 13 Tocilizumab Summary of Treatment Administered

Study Treatment Name:	Tocilizumab
Dosage Formulation:	Concentrate for solution for IV infusion
Unit Dose Strength(s)/Dosage Level(s):	200 mg/10 mL
Dose:	8 mg/kg IV
Route of Administration:	IV
Dosing Instructions:	see Pharmacy Manual
Packaging and Labeling:	Study treatment will be provided in a carton box (one labeled vial per box). Each carton box will be labeled as required per country requirement.

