Once the IV schedule has shown RO7172508 preliminary clinical activity, defined by partial response (PR) or better, according to RECIST v. 1.1 (Appendix 6), or the MTD has been established and is equal to or above 2 mg, the SC multiple-ascending dose-finding cohorts could be initiated. The starting-dose and regimen (QW or Q3W) for SC administration will be proposed based on the evaluation of the safety and PK data observed following IV administration but will not exceed the highest safe dose tested in the IV Q3W dose escalation; however, due to practical considerations, a minimum dose of 2 mg is defined for a single SC administration. In addition, the QW SC starting-dose will not exceed one third of the IV MTD or of the highest safe IV dose tested.

Dose escalation in the SC treatment group will proceed until the SC MTD/OBD has been determined (see Section 4.1.2). *If the SC treatment group is started Q3W at a dose <6*

mg, the QW schedule can be evaluated once the dose is ≥ 6 mg. Data from this treatment group will establish if the SC route of administration, which will have a lower C_{max} than IV after first administration, can show comparable efficacy and/or comparable or improved safety profile of a TCB either QW and/or Q3W.

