Dose Level	Dose (mg)	Dose-Increment if no DLT (%)	Next Dose if no DLT (mg)
1	1.6	100	3.2
2	3.2	97	6.3
3	6.3	90	12
4	12	67	20
5	20	100	40
6	40	100	80
7	80	88	150
8	150	100	300
9	300	33	400
10	400	N/A	N/A

Dose-frequency may be adjusted depending on the emerging PK data for RO7172508 and given an appropriate previously observed safety and tolerability profile. Different dosing schedules (e.g., non-fractionated and/or fractionated dosing) may be tested in parallel. If a decision is made to adjust the dosing schedule during the course of dose-escalation, the mCRM-EWOC algorithm will be updated with the available participant data and adapted to account for any difference in exposure of the new schedule. The initial starting-dose will not exceed a dose already tested and considered safe. Safety and DLT window may also be adapted. If fractionated dosing is implemented, the DLT window will be extended until the end of the cycle in which the planned full dose is administered.

- Dose-escalation to SC MTD

Once an MTD or OBD has been defined, or relevant clinical activity is seen (e.g., PR or better according to RECIST) for IV route of administration and schedule, SC administration will be tested. The starting dose *and regimen* for SC will be proposed based on the evaluation of the safety and efficacy data observed following IV administration; however, due to practical considerations, a minimum dose of 2 mg is defined for a single SC administration (Section 4.3).

In the QW cohorts, RO7172508 will be administered *three times per cycle (i.e. QW)*, with a maximum starting-dose of one third of the RO7172508 IV MTD dose or, in case MTD has not been reached, of the highest safe dose ≥ 6 mg tested in the IV dose-escalation part. *For a Q3W regimen the starting dose will not exceed the highest safe dose tested in the IV Q3W dose escalation.*

The maximum allowed dose will be 160 mg QW *or* 400 mg Q3W (flat dose). Different dosing schedules (e.g., non-fractionated and/or fractionated dosing) may be tested.

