4.3 DOSE JUSTIFICATION

4.3.1 RO7172508

The entry-into-human starting flat dose of 65 μ g was derived from incorporating an integrated approach, which was informed by in vitro activity in high-CEA expressing tumor cells as well as clinical safety experience with *cibisatamab* (see [RO7172508 Investigator's Brochure](#)). Compared to a classical minimum anticipated biological effect level (MABEL) approach, the approach used here reduces the number of participants exposed to sub-therapeutic doses of RO7172508 while ensuring that the starting-dose is in a safe range.

Taking into account 20-fold potency increase, a 400 μ g dose of RO7172508 would be equivalent to 8 mg dose of *cibisatamab* (dose with no relevant cytokine increase documented and no Grade 3-related AEs reported).

Based on the available data, the Sponsor has defined the following intermediate doses in Part I:

- Second cohort: 160 μ g
- Third cohort: 400 μ g
- Fourth cohort: 800 μ g
- Fifth and last cohort: 1.6 mg

Incremental dose-increases may be altered based on emerging PK, PD and safety data but will not exceed 3-fold. If there is no safety concern reported in Part I during the safety

observation period (stopping rule: any RO7172508-related event of Grade ≥ 2 toxicity reported within the DLT window), Part II of the study will start with a dose of 1.6 mg. Dose-escalation for Part II will follow the mCRM-EWOC design (see Section 4.1.2).

A maximum dose of 400 mg Q3W of RO7172508 has been defined. The C_{\max} observed at Cycle 1 of 400 mg (MTD) *cibisatamab* was 113 $\mu\text{g/mL}$. Assuming a potency factor of 20, an equivalent RO7172508 C_{\max} of 5.6 $\mu\text{g/mL}$ is estimated to be achieved by 25 mg. The clinical potency may differ from the in vitro levels; therefore, a maximum dose of 400 mg has been defined to allow this to be tested. The dose-escalation will only take place once a full evaluation of safety data has taken place and the dose-increment levels may be reduced to ensure the participant's safety. Dose-fractionation may also be implemented in Cycle 1 where a dose not exceeding 400 mg will be administered over one cycle e.g., 40 mg on Day 1, 120 mg on Day 8 and 240 mg on Day 15. The maximum SC dose administered QW will be 160 mg QW which is 480 mg over a three-week period/cycle. By applying a conservative bioavailability of $\sim 80\%$ this would equate to 400 mg Q3W IV.

Further details are provided in the [RO7172508 Investigator's Brochure](#).

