1.2.3 Dose Grid

The following dose grid has been used: from 0.5, to 10 by 0.1, from 11 to 20 by 1, 25, 27, from 30 to 100 by 5, 120, 150 to 400 by 50.

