1.4.1 Dose-toxicity Scenarios

In these simulations (Figure 2), the starting dose of 0.5 mg is assumed. Scenario 1 reflects the current expected toxicity of this compound. The others are intermediate or extreme scenarios. The MTD (upper 35% DLT toxicity interval) ranges from 69 mg (low MTD) to 438 mg (illustrating a scenario for which toxicities are expected only at the highest dose).

Figure 2 Dose Toxicity Scenarios

[figure not shown]

Table 2: Scenarios Parameters

Scenario	Target Dose Interval, mg	Parameters
1	48-75	alpha = -0.11, beta = 1.74
2	136-199	alpha = -2, beta = 2
3	247-299	alpha = -5, beta = 4
4	82-121	alpha = -1, beta = 2
5	375-438	alpha = -8, beta = 5
6	23-69	alpha = -0.36, beta = 0.7

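### Table 11 limits Part II subcutaneous dosing to 160 mg without naming a schedule, but Section 4.1.2.2 allows 160 mg weekly or 400 mg every three weeks

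*Combined protocol and SAP*

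**What the plan says.** Section 6.1, Table 11, gives a single SC dose range for Part II: "2 mg up to a maximum of 160 mg SC". The table has no schedule row and refers to the Pharmacy Manual for dosing instructions.

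Section 4.1.2.2, in the part on escalation to the SC MTD, gives two maxima: 160 mg for QW, or "400 mg Q3W (flat dose").

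Section 4.3.1 explains the first of these: "The maximum SC dose administered QW will be 160 mg QW which is 480 mg over a three-week period/cycle". It then applies a bioavailability of about 80% and equates the result to 400 mg Q3W IV.

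SC Q3W is a regimen in current use in the plan. The synopsis and Section 4.1 offer QW or Q3W for SC, and Table 7 is a full schedule of assessments for SC Q3W cohorts. Section 3 makes determination of the MTD and/or OBD a primary objective for the SC route as well as the IV route.

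**The concern.** A maximum dose in the treatment table of a first-in-human study is an operating limit. Sites, pharmacists and ethics committees may read it there without going to the escalation section. Here it disagrees with the escalation section for one of the two SC regimens.

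If Table 11 is followed, SC Q3W escalation ends at 160 mg, and an SC Q3W MTD above that dose would not be found. If Section 4.1.2.2 is followed, any SC Q3W cohort above 160 mg lies outside the treatment table. Section 8 permits no protocol waivers, and Section 9.5 requires all deviations to be listed. The status of such a cohort should not depend on which section is consulted.

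**Working it through.** **Inputs**

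| Item | Value | Source |
|---|---|---|
| SC maximum, no schedule given | 160 mg | Section 6.1, Table 11 |
| SC maximum, QW | 160 mg | Section 4.1.2.2 |
| SC maximum, Q3W | 400 mg | Section 4.1.2.2 |
| Cycle total at the QW maximum | 480 mg | Section 4.3.1 |
| Assumed SC bioavailability | about 80% | Section 4.3.1 |
| Provisional dose steps | 1.6 to 400 mg | Section 4.1.2.2, Table 9 |

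**Step 1: reproduce the plan's figure.** Three weekly doses of 160 mg give 3 × 160 = 480 mg per cycle, as stated. At 80% bioavailability this is 480 × 0.80 = 384 mg, against the stated 400 mg. The result is 4% low, and exactly 400 mg would need 400/480 = 83.3%. The plan writes an approximate 80%, so this is rounding and has no bearing on the point.

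**Step 2: what the 160 mg figure means.** It is a per-injection limit justified by three injections per cycle. That argument supports 160 mg three times per cycle. It gives no reason for 160 mg once per cycle.

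**Step 3: size of the conflict for Q3W.**
- Ratio of the two ceilings: 160/400 = 0.40, so the Section 4.1.2.2 limit is 2.5 times the one in Table 11.
- IV-equivalent per cycle at 80% bioavailability: 160 × 0.80 = 128 mg under Table 11, and 400 × 0.80 = 320 mg under Section 4.1.2.2.
- Table 9 steps above 160 mg: 300 and 400 mg. Table 9 is not labelled as an SC grid, so this is an illustration that assumes the same steps are used for SC.

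**Step 4: search for a reconciling statement.** No section limits SC Q3W to 160 mg. The Q3W starting-dose rule in Section 4.1.2.2 refers only to the highest safe IV Q3W dose. Section 6.1 says nothing that links the two ceilings. Both conflicting statements are in the current text, so the point does not rest on the amendment history. The version 4 rationale says that SC Q3W was added in that amendment. It is plausible that Table 11 was not updated to match, but that is an inference and the point does not need it.

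**The case against.** **The intended limit can be recovered.** Section 4.1.2.2 is explicit, Section 4.3.1 ties 160 mg to QW, and Table 11 is a summary that gives no schedule for IV either. Escalation is decided jointly by the sponsor and investigators, guided by the dose-escalation model, and nothing says that Table 11 overrides Section 4.1.2.2. This stands as a limit on the harm. It does not remove the conflict, because one of the two numbers is wrong for SC Q3W.

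**The ceiling may never bind.** SC cohorts are optional, SC Q3W is one of two regimens, and the amendment rationale motivates it by a low IV MTD, between 2 and 6 mg. Section 4.3.1 puts the potency-equivalent of the comparator's MTD at 25 mg, and 160 mg is 160/25 = 6.4 times that. This also stands. However, neither Section 4.1 nor Section 4.1.2.2 restricts SC Q3W to low doses.

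**160 mg might be deliberate,** for example because of injection volume. At the 20 mg/mL strength in Table 11, 160 mg is 160/20 = 8 mL and 400 mg is 400/20 = 20 mL. The documents give no such reason. If it were the reason, Section 4.1.2.2 would be the text to correct, so one statement has to change either way.

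**Stronger readings that the documents do not support.** A reader might use the Appendix 8 scenarios and selected-MTD quantiles to estimate how often a 160 mg SC ceiling would cut escalation short. Appendix 8 simulates the IV escalation only, and Section 4.1.2.2 says the model will be adapted for SC to reflect different exposure, with more uncertainty. Those results do not measure SC Q3W.

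A reader might also infer from Section 4.1 ("the QW schedule can be evaluated once the dose is" at least 6 mg) that QW could open above the IV-based cap on its starting dose. That cap is stated just before, without qualification: "the QW SC starting-dose will not exceed one third of the IV MTD or of the highest safe IV dose tested". Not repeating it does not revoke it. A rule barring QW whenever the IV MTD is below 6 mg would be a new restriction, which is for the sponsor to decide.

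**Conclusion.** The contradiction is real and lies in current text. For SC Q3W, Table 11 gives a ceiling of 160 mg and Section 4.1.2.2 gives 400 mg, so the table stands at 40% of the escalation limit. It has a practical effect only if SC Q3W is opened and goes above 160 mg, and the documents do not allow a probability to be put on that.

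The error is in the conservative direction. It should not be read as a risk of overdosing, nor as showing that the SC objective would fail: that objective is the MTD and/or OBD, and Table 11 is not stated to govern escalation. No sample size, model or operating characteristic is affected. The conclusion assumes that Section 4.1.2.2 states the intended limit, which the derivation in Section 4.3.1 supports. The Pharmacy Manual, to which Table 11 refers, was not available.

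**What to change.** In Section 6.1, Table 11, rewrite the Part II SC dose entry to give both regimens: SC minimum 2 mg; maximum 160 mg if QW, 400 mg if Q3W. If the sponsor did intend 160 mg as the limit for Q3W as well, correct Section 4.1.2.2 instead and give the reason.

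The cost is the wording of one table cell. The change raises no limit set in Sections 4.1, 4.1.2.2 or 4.3.1, and it needs no new data, assessments or participants. The Pharmacy Manual should be checked for the same figure.

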6.1.1 Pre-medication

All pre-medications should be captured as concomitant medications in the participant's electronic Case Report Form (eCRF). If during dose-escalation Grade ≥ 2 IRRs/CRS or tumor inflammatory events occur in the majority of participants, the utility of prophylactic pre-medication with systemic corticosteroids in preventing such events may be tested using the regimen as outlined in [Table 14](#) (flat dosing) and [Table 15](#) (for fractionated dosing). If successful, this regimen will then be used in future cohorts.

In the event that the change in the route of administration from IV to SC does not mitigate the tumor inflammatory events or IRRs, then the same steroid regimen may be implemented as described in [Table 14](#) and [Table 15](#). These regimens are based on the expected duration of inflammatory events and they may be reduced or modified based on emerging data. *Also, they may be extended from Cycle 1 to subsequent cycles, in case tumor inflammation and/or IRR occur at later cycles.* Pre-medication may also include 1000 ml saline, 50 mg indomethacin (or equivalent non-steroidal anti-inflammatory [NSAID]), and 50 mg diphenhydramine (or equivalent H1 antagonist).

Table 14 Steroid Use on Cycle 1 of RO7172508 Infusion to be implemented in the event of frequent IRR/CRS or gastrointestinal RO7172508-related toxicity occurrence after first administration

Timing	Dose
C1D1: 4 to 6 hours before RO7172508 infusion	1 mg/kg methylprednisolone IV* 1 g paracetamol PO TID 2 mg loperamide PO
C1D1: approximately 2 hours after RO7172508 infusion	1 mg/kg methylprednisolone IV*
C1D2: approximately 24 hours post-RO7172508 EOI	1 mg/kg prednisone IV/PO* 1 g paracetamol PO TID 2 mg loperamide PO**
C1D3: approximately 48 hours post-RO7172508 EOI	0.5 mg/kg prednisone IV/PO* 1 g paracetamol PO TID
C1D4: approximately 72 hours post-RO7172508 EOI	0.5 mg/kg prednisone IV/PO* 1 g paracetamol PO TID

C: Cycle; D: Day; EOI: end of infusion; IV: intravenous; PO: oral; TID: 3 times a day.

* rounded up to next multiple of 10 mg (or equivalent doses of mid acting steroids)

** subsequent treatment with loperamide only to be given as clinically indicated

Table 15 Steroid Use on Cycle 1 of RO7172508 or gastrointestinal RO7172508-related toxicity to be implemented in the event of frequent IRR/CRS persisting despite dose fractionation

Timing	Dose
C1D1: 4 to 6 hours before RO7172508 infusion	1 mg/kg methylprednisolone IV* 1 g paracetamol PO TID 2 mg loperamide PO
C1D1: approximately 2 hours post-RO7172508 EOI	1 mg/kg prednisone IV/PO 1 g paracetamol PO TID
C1D2: approximately 24 hours post-RO7172508 EOI	1 mg/kg prednisone IV/PO
C1D8: 60 minutes before RO7172508 infusion	1 mg/kg methylprednisolone IV* 1 g paracetamol PO TID 2 mg loperamide PO**
C1D8: approximately 2 hours post-RO7172508 EOI	0.5 mg/kg prednisone IV/PO 1 g paracetamol PO TID
C1D9: approximately 24 hours post-RO7172508 EOI	0.5 mg/kg prednisone IV/PO
C1D15: 60 minutes before RO7172508 infusion	1 mg/kg methylprednisolone IV* 1 g paracetamol PO TID 2 mg loperamide PO **
C1D15: approximately 2 hours post-RO7172508 EOI	1 mg/kg prednisone IV/PO 1 g paracetamol PO TID
C1D16: approximately 24 hours post-RO7172508 EOI	0.5 mg/kg prednisone IV/PO

C: Cycle; D: Day; EOI: end of infusion; IV: intravenous; PO: oral; TID: 3 times a day.

* rounded up to next multiple of 10 mg (or equivalent doses of mid acting steroids)

** subsequent treatment with loperamide only to be given as clinically indicated

In addition to the above mentioned premedication regimens, additional premedication may be implemented after agreement between Sponsor and Investigators for prophylaxis of RO7172508-related toxicity at cycle 1 and/or at subsequent cycles:

- *From 30 to 60 minutes before administration of RO7172508, 5-HT₃-receptor antagonist administration (preferably a long acting antagonist such as palonosetron 500 µg);*
- *Budesonide 9mg daily to start 3 days before first RO7172508 and to be continued up to 7 days after first RO7172508 administration.*

Subsequent RO7172508 Infusions

Participants who experienced a Grade 2 IRR or other RO7172508-related toxicity within 24 hours of RO7172508 administration on a previous infusion, should be pre-medicated for subsequent infusions. The regimen indicated in [Table 14](#) will be recommended for subsequent cycles, however in lieu of IV methylprednisolone administration, an equal oral dose of methylprednisolone (or equivalent) can be used. Similarly, the additional premedication regimens may be moved to subsequent cycles to prevent recurrence of the toxicity that occurred in Cycle 1. Premedication regimens for subsequent cycles may be reduced or omitted in case of \leq Grade 1 events in the previous cycle.

For participants who experience an IRR-like reaction with a single and isolated symptom, such as fever that occurs within 24 hours after the study treatment infusion was completed, the use of pre-medication such as paracetamol, anti-histamine, and corticosteroids is not foreseen prior to subsequent RO7172508 administrations. The event will be reported as a single AE (e.g., fever). Pre-medication with corticosteroids of those participants at subsequent infusions needs approval from the Sponsor and the treatment and management at the time of an event is at the discretion of the Investigator. Pre-medication may be changed based on emerging data and the regimens described above should be considered as the maximum suggested regimens. After collecting information on the effectiveness of the above mentioned premedication regimens scheduling and dose intensities may be reduced but not increased.

Premedication Prior to Obinutuzumab Administration

The use of corticosteroids, analgesics, non-steroidal anti-inflammatory drugs (NSAIDs) and/or antihistamines is required to minimize expected IRR reactions associated with the administration of obinutuzumab. Pre-medication must be administered prior to obinutuzumab administration. A list of the mandatory pre-medications is provided in [Table 16](#).

Hypotension may occur as a result of an IRR adverse event. Therefore, it is recommended that antihypertensive drugs not be given on the morning of, and throughout the infusion of obinutuzumab, even if clinically indicated. Patients with a history of cardiac disease should be monitored closely.

Table 16 *Premedication Requirements for Obinutuzumab*

Pre-Medication	Timing of Administration
Prednisolone 100 mg administered by IV infusion (or equivalent)	At least 60 minutes prior to the obinutuzumab infusion
Analgesic/anti-pyretic (e.g., paracetamol/oral acetaminophen 500 –1000 mg) administered orally or by IV infusion	At least 30 minutes prior to the obinutuzumab infusion
Antihistamine (e.g., oral diphenhydramine 50 –100 mg) administered orally or by IV infusion (or an alternative anti-histamine at an adequate dose)	At least 60 minutes prior to the obinutuzumab infusion

